	
3b) Subjects with epidermal growth factor receptor (EGFR) mutations or alkaline phosphatase (ALK) translocations are required to have received prior therapy with appropriate tyrosine kinase inhibitor (TKI); prior platinum-based chemotherapy is not required for this specific patient population.
 
 4. Presence of radiographically measurable disease as defined by RECIST 1.1. 5. Eastern Cooperative Oncology Group (ECOG) performance status of 0 or 1. 6. Completion of all therapy (including surgery, radiotherapy, chemotherapy, immunotherapy, or investigational therapy) for the treatment of cancer \geq 2 weeks before the start of study therapy and recovered (ie, Grade \leq 1 or baseline) from AEs associated with prior cancer therapy. Note: Subjects with Grade \leq 2 neuropathy or Grade \leq 2 alopecia are an exception to the latter criterion and may qualify for the study. 7. Women who are sexually active and can bear children must agree to use acceptable forms of contraception during the study and for 90 days after the last dose of acalabrutinib or 120 days after the last dose of pembrolizumab, whichever is longer. Note: Acceptable forms of contraception are defined in Section 3.10.6. 8. Men who are sexually active and can beget children must agree to use acceptable forms of contraception during the study and for 90 days after the last dose of acalabrutinib or 120 days after the last dose of pembrolizumab, whichever is longer. 9. Men must agree to refrain from sperm donation during the study and for 90 days after the last dose of acalabrutinib or 120 days after the last dose of pembrolizumab, whichever is longer. 10. Able to provide tissue for biomarker analysis from either an archived tissue sample or newly obtained core or excisional biopsy of a tumor lesion not previously irradiated. 11. Willing and able to participate in all required evaluations and procedures in this study protocol including swallowing capsules without difficulty. 12. Ability to understand the purpose and risks of the study and provide signed and dated informed consent and authorization to use protected health information (in accordance with national and local patient privacy regulations).
Exclusion Criteria:	
 1. Prior malignancy (other than lung cancer), except for adequately treated basal cell or squamous cell skin cancer, in situ cancer, or other cancer from which the subject has been disease free for \geq 2 years. 2. Known central nervous system metastases and/or carcinomatous meningitis. Brain metastases, but not carcinomatous meningitis, are allowed if they had been

	
previously treated (either surgically resected or by radiation therapy) and had remained stable by repeat imaging ≥ 4 weeks after treatment before enrolling on this protocol.
 
 
3. Significant cardiovascular disease such as uncontrolled or symptomatic arrhythmias, congestive heart failure, or myocardial infarction within 6 months of screening, or any Class 3 or 4 cardiac disease as defined by the New York Heart Association Functional Classification, or corrected QT interval (QTc) > 480 msec at screening. 
4. Malabsorption syndrome, disease significantly affecting gastrointestinal function, or resection of the stomach or small bowel, symptomatic inflammatory bowel disease, partial or complete bowel obstruction, or gastric restrictions and bariatric surgery, such as gastric bypass. 
5. Prior therapy with any inhibitor of BTK, protein kinase B (AKT), Janus kinase (JAK), mammalian target of rapamycin (mTOR), phosphatidylinositol-3 kinase (PI3K), or spleen tyrosine kinase (SYK). 
6. Prior therapy with an anti-PD-1, anti-PD-L1, anti-PD ligand 2 (anti-PD-L2), anti-CD137, or anti-cytotoxic T-lymphocyte-associated antigen-4 (CTLA-4) antibody (including ipilimumab, tremelimumab, nivolumab, pembrolizumab, MPDL3280A or any other antibody or drug specifically targeting T-cell co-stimulation or checkpoint pathways). 
7. Receiving ongoing immunosuppressive therapy, including systemic or enteric corticosteroids except for non-systemically absorbed treatments (such as inhaled or topical steroid therapy for asthma, chronic obstructive pulmonary disease, or allergic rhinitis) within 7 days before the first dose of pembrolizumab. 
8. Active autoimmune disease that has required systemic treatment in past 2 years (ie, with use of disease modifying agents, corticosteroids or immunosuppressive drugs). Note: Replacement therapy (eg, thyroxine, insulin, or physiologic corticosteroid replacement therapy for adrenal or pituitary insufficiency) is not considered a form of systemic treatment. 
9. Has evidence of active, non-infectious pneumonitis or a history of interstitial lung disease. 
10. History of severe allergic, anaphylactic, or other hypersensitivity reactions to chimeric or humanized antibodies or fusion proteins. 
11. History of bleeding diathesis (eg, hemophilia or von Willebrand disease). 
12. Requires treatment with a strong cytochrome P450 3A (CYP3A) inhibitor/inducer. 
13. Requires or receiving anticoagulation with warfarin or equivalent vitamin K antagonists (eg, phenprocoumon) within 7 days of first dose of study drug.
--	---

	
14. Requires treatment with proton-pump inhibitors (eg, omeprazole, esomeprazole, lansoprazole, dexlansoprazole, rabeprazole, or pantoprazole).15. Known history of human immunodeficiency virus (HIV) or active infection with hepatitis C virus (HCV) or hepatitis B virus (HBV), or any active infection requiring systemic therapy within 2 weeks before first dose of study drug. Note: Subjects receiving prophylactic antibiotics (eg, for prevention of a urinary tract infection or chronic obstructive pulmonary disease) are eligible.16. History of stroke or intracranial hemorrhage within 6 months before the first dose of study drug.17. Major surgical procedure within 28 days of first dose of study drug. Note: If a subject had major surgery, they must have recovered adequately from any toxicity and/or complications from the intervention before the first dose of study drug.18. Prior allogeneic bone marrow transplantation or prior solid organ transplantation.19. Has received a live vaccine within 30 days of planned start of study therapy.20. Absolute neutrophil count (ANC) < $1.5 \times 10^9/L$ or platelet count < $100 \times 10^9/L$ or hemoglobin < 8.0 g/dL.21. Total bilirubin > $1.5 \times ULN$; or aspartate aminotransferase (AST) or alanine aminotransferase (ALT) > $3.0 \times ULN$22. Estimated creatinine clearance of < 30 mL/min, calculated using the formula of Cockroft and Gault ($140 - \text{Age}) \cdot \text{Mass (kg)} / (72 \cdot \text{creatinine mg/dL})$; multiply by 0.85 if female.23. Breastfeeding or pregnant or expecting to conceive or father children within the projected duration of the trial, starting with the screening visit through 120 days after the last dose of trial treatment.24. Is currently participating in a clinical trial and receiving study therapy or has participated in a study of an investigational agent and received study therapy or used an investigational device within 4 weeks of the first dose of treatment.25. Immediate family members of the sponsor personnel or site staff directly involved with the conduct of this protocol are excluded from participating on this study.26. Presence of a gastrointestinal ulcer diagnosed by endoscopy within 3 months prior to screening.27. Serologic status reflecting active hepatitis B or C infection. Subjects with hepatitis B core antibody positive who are surface antigen negative or who are hepatitis C antibody positive will need to have a negative polymerase chain reaction (PCR) result before enrollment. Those who are hepatitis B surface antigen positive or hepatitis B PCR positive and those who are hepatitis C PCR positive will be excluded.
--	---

Dose Regimen/Route of Administration:	
Acalabrutinib is provided as hard gelatin capsules for oral administration.
 
KEYTRUDA® (pembrolizumab) for injection is provided as a 100 mg/4 mL (25 mg/mL) solution in a single-use vial or as a lyophilized powder for reconstitution (50 mg/vial). It is administered as an IV infusion over 30 minutes.
 
Arm 1: Pembrolizumab 200 mg every 3 weeks (Q3W)
 
Arm 2:
 
  
 Dose Level	Acalabrutinib	Pembrolizumab	
   
 Starting Dose	100 mg BID PO	200 mg Q3W IV	
 
 Level -1	100 mg QD PO	200 mg Q3W IV	
 
 Level -2	50 mg BID PO	200 mg Q3W IV	
  
 
Abbreviations: BID = twice per day; IV = intravenous, PO = oral; Q3W = every 3 weeks
	Dose Level	Acalabrutinib	Pembrolizumab	Starting Dose	100 mg BID PO	200 mg Q3W IV	Level -1	100 mg QD PO	200 mg Q3W IV	Level -2	50 mg BID PO	200 mg Q3W IV
Dose Level	Acalabrutinib	Pembrolizumab											
Starting Dose	100 mg BID PO	200 mg Q3W IV											
Level -1	100 mg QD PO	200 mg Q3W IV											
Level -2	50 mg BID PO	200 mg Q3W IV											
Concomitant Medications:	
The concomitant use of strong inhibitors/inducers of CYP3A with acalabrutinib should be avoided when possible. The effect of agents that reduce gastric acidity (eg, proton-pump inhibitors, H2-receptor antagonists or antacids) on acalabrutinib absorption was evaluated in a healthy volunteer study (ACE-HV-004). Results from this study indicate that subjects should avoid the use of calcium carbonate-containing drugs or supplements and short-acting H2-receptor antagonists for a period of at least 2 hours before and after taking acalabrutinib. Use of omeprazole or esomeprazole or any other proton-pump inhibitors while taking acalabrutinib is not recommended due to a potential decrease in study drug exposure.
												
Statistical Methods:	
Descriptive statistics (including means, standard deviations, and medians for continuous variables and proportions and confidence intervals [CIs] for discrete variables) will be used to summarize data as appropriate.
 
Statistical Basis for the Sample Size
 
For the interim safety analysis (DLT review), enrollment of [REDACTED] in the combination arm for DLT review is consistent with sample sizes used in oncology studies for determination of maximum tolerated dose (MTD). The trial employs the standard National Cancer Institute definition of MTD (dose associated with DLT in \leq [REDACTED]). Provided the DLT review period is cleared in the combination arm and the study is not stopped early
												

	
due to futility or toxicity (Section 5.5), then up to 31 additional subjects will be added per arm.
 
The sample size for this 2-arm trial was determined by a Z-test for normal approximation of binomial distribution, based on one-sided $\alpha = 0.10$, 80% power, with projected response rates of 40% in pembrolizumab/acalabrutinib arm and 18% in pembrolizumab arm.
 
[REDACTED]

--	--

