3.3.2 Exclusion Criteria

Subjects will be ineligible for this study if they meet **any** of the following criteria:

1. Prior malignancy (other than lung cancer), except for adequately treated basal cell or squamous cell skin cancer, in situ cancer, or other cancer from which the subject has been disease free for \geq 2 years.
2. Known central nervous system metastases and/or carcinomatous meningitis. Brain metastases, but not carcinomatous meningitis, are allowed if they had been previously treated (either surgically resected or by radiation therapy) and had remained stable by repeat imaging \geq 4 weeks after treatment before enrolling on this protocol.
3. Significant cardiovascular disease such as uncontrolled or symptomatic arrhythmias, congestive heart failure, or myocardial infarction within 6 months of screening, or any Class 3 or 4 cardiac disease as defined by the New York Heart Association Functional Classification, or corrected QT interval (QTc) $>$ 480 msec at screening.
4. Malabsorption syndrome, disease significantly affecting gastrointestinal function, or resection of the stomach or small bowel, symptomatic inflammatory bowel disease, partial or complete bowel obstruction, or gastric restrictions and bariatric surgery, such as gastric bypass.
5. Prior therapy with any inhibitor of BTK, AKT, JAK, mTOR, PI3K, or SYK.
6. Prior therapy with an anti-PD-1, anti-PD-L1, anti-PD-L2, anti-CD137, or anti-CTLA-4 antibody (including ipilimumab, tremelimumab, nivolumab, pembrolizumab, MPDL3280A or any other antibody or drug specifically targeting T-cell co-stimulation or checkpoint pathways).

7. Receiving ongoing immunosuppressive therapy, including systemic or enteric corticosteroids except for non-systemically absorbed treatments (such as inhaled or topical steroid therapy for asthma, chronic obstructive pulmonary disease, or allergic rhinitis) within 7 days before the first dose of pembrolizumab.
8. Active autoimmune disease that has required systemic treatment in past 2 years (ie, with use of disease modifying agents, corticosteroids or immunosuppressive drugs). Note: Replacement therapy (eg, thyroxine, insulin, or physiologic corticosteroid replacement therapy for adrenal or pituitary insufficiency) is not considered a form of systemic treatment.
9. Has evidence of active, non-infectious pneumonitis or a history of interstitial lung disease.

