10. History of severe allergic, anaphylactic, or other hypersensitivity reactions to chimeric or humanized antibodies or fusion proteins.
11. History of bleeding diathesis (eg, hemophilia or von Willebrand disease).
12. Requires treatment with a strong CYP3A inhibitor/inducer.
13. Requires or receiving anticoagulation with warfarin or equivalent vitamin K antagonists (eg, phenprocoumon) within 7 days of first dose of study drug.
14. Requires treatment with proton-pump inhibitors (eg, omeprazole, esomeprazole, lansoprazole, dexlansoprazole, rabeprazole, or pantoprazole).
15. Known history of HIV or active infection with HCV or HBV, or any active infection requiring systemic therapy within 2 weeks before first dose of study drug. Note: Subjects receiving prophylactic antibiotics (eg, for prevention of a urinary tract infection or chronic obstructive pulmonary disease) are eligible.
16. History of stroke or intracranial hemorrhage within 6 months before the first dose of study drug.
17. Major surgical procedure within 28 days of first dose of study drug. Note: If a subject had major surgery, they must have recovered adequately from any toxicity and/or complications from the intervention before the first dose of study drug.
18. Prior allogeneic bone marrow transplantation or prior solid organ transplantation.
19. Has received a live vaccine within 30 days of planned start of study therapy.
20. ANC $< 1.5 \times 10^9/L$ or platelet count $< 100 \times 10^9/L$ or hemoglobin $< 8.0 \text{ g/dL}$.
21. Total bilirubin $> 1.5 \times \text{ULN}$; and AST or ALT $> 3.0 \times \text{ULN}$.
22. Estimated creatinine clearance of $< 30 \text{ mL/min}$, calculated using the formula of Cockroft and Gault $(140 - \text{Age}) \cdot \text{Mass (kg)} / (72 \cdot \text{creatinine mg/dL})$; multiply by 0.85 if female.
23. Breastfeeding or pregnant or expecting to conceive or father children within the projected duration of the trial, starting with the screening visit through 120 days after the last dose of trial treatment.
24. Is currently participating in a clinical trial and receiving study therapy or has participated in a study of an investigational agent and received study therapy or used an investigational device within 4 weeks of the first dose of treatment.
25. Immediate family members of the sponsor personnel or site staff directly involved with the conduct of this protocol are excluded from participating on this study.

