3.10 PRECAUTIONS

3.10.1 Transaminase Elevations for Acalabrutinib in Combination with Pembrolizumab

Serum transaminase elevations (including elevations of AST and/or ALT) may be increased in severity and frequency in subjects exposed to the combination of acalabrutinib and pembrolizumab, as compared with subjects exposed to pembrolizumab monotherapy and subjects exposed to acalabrutinib monotherapy. Routine monitoring for serum transaminase elevations must follow the Schedule of Assessments (serum chemistry lab assessments). Dosing delays and modifications for subjects with serum transaminase elevations must follow guidance provided in [Section 3.8](#).

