2.3 Dose Modifications

Withhold KEYTRUDA for any of the following:

- Grade 2 pneumonitis [see *Warnings and Precautions* (5.1)]
- Grade 2 or 3 colitis [see *Warnings and Precautions* (5.2)]
- Grade 3 or 4 endocrinopathies [see *Warnings and Precautions* (5.4)]
- Grade 2 nephritis [see *Warnings and Precautions* (5.5)]
- Aspartate aminotransferase (AST) or alanine aminotransferase (ALT) greater than 3 and up to 5 times upper limit of normal (ULN) or total bilirubin greater than 1.5 and up to 3 times ULN
- Any other severe or Grade 3 treatment-related adverse reaction [see *Warnings and Precautions* (5.6)]

Resume KEYTRUDA in patients whose adverse reactions recover to Grade 0-1.

Permanently discontinue KEYTRUDA for any of the following:

- Any life-threatening adverse reaction (excluding endocrinopathies controlled with hormone replacement therapy)
- Grade 3 or 4 pneumonitis or recurrent pneumonitis of Grade 2 severity [see *Warnings and Precautions* (5.1)]
- Grade 3 or 4 nephritis [see *Warnings and Precautions* (5.5)]
- AST or ALT greater than 5 times ULN or total bilirubin greater than 3 times ULN
 - For patients with liver metastasis who begin treatment with Grade 2 AST or ALT, if AST or ALT increases by greater than or equal to 50% relative to baseline and lasts for at least 1 week
- Grade 3 or 4 infusion-related reactions [see *Warnings and Precautions* (5.7)]

- Inability to reduce corticosteroid dose to 10 mg or less of prednisone or equivalent per day within 12 weeks
- Persistent Grade 2 or 3 adverse reactions (excluding endocrinopathies controlled with hormone replacement therapy) that do not recover to Grade 0-1 within 12 weeks after last dose of KEYTRUDA
- Any severe or Grade 3 treatment-related adverse reaction that recurs [see *Warnings and Precautions (5.6)*]

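### Exclusion criterion 21 joins the bilirubin and AST/ALT limits with *or* in the synopsis but with *and* in Section 3.3.2, so the section that governs eligibility admits isolated liver abnormalities of any size

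*Protocol*

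**What the plan says.** Criterion 21 appears twice in the current protocol.

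- **Study Synopsis, Exclusion Criteria, item 21.** After the bilirubin limit of 1.5 × ULN the text continues "or aspartate aminotransferase (AST) or alanine aminotransferase (ALT", with a limit of 3.0 × ULN. Either abnormality on its own excludes.
- **Section 3.3.2, item 21.** The criterion reads "Total bilirubin $> 1.5 \times \text{ULN}$; and AST or ALT $> 3.0 \times \text{ULN". The item number and both thresholds are the same, but the joining word is *and*.

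The list in Section 3.3.2 opens with "Subjects will be ineligible for this study if they meet any of the following criteria", so meeting one numbered item is enough to exclude. Within item 21, the joining word decides what counts as meeting it.

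Section 4.1.5 says that eligibility is assessed against Section 3.3. The Amendment 4 summary records a change to exclusion 6 and none to exclusion 21, so it does not explain the difference.

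**The concern.** The two versions define different trial populations. Under the synopsis, no subject enters with AST or ALT above 3.0 × ULN or with bilirubin above 1.5 × ULN. Under Section 3.3.2, AST and ALT have no upper limit as long as bilirubin is at or below 1.5 × ULN, and bilirubin has no upper limit as long as AST and ALT are at or below 3.0 × ULN.

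The liver is the organ of concern in this trial. Section 3.10.1, added by Amendment 4, states that transaminase elevations "may be increased in severity and frequency in subjects exposed to the combination of acalabrutinib and pembrolizumab" compared with either drug alone. Arm 1 subjects may also receive the combination after progression (Section 3.0), so the criterion governs exposure in both arms.

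Three things are at stake: the safety of subjects who start with marked liver abnormality, consistency between sites that work from different pages, and the interpretation of hepatic events. Safety is a primary objective (Section 2.1), and related Grade ≥ 3 toxicity counts as a DLT (Section 3.7).

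**Working it through.** The protocol gives no figure to reproduce here. The check compares the two rules and looks for anything else that would close the gap.

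**1. Truth table.** Let B mean total bilirubin > 1.5 × ULN, and T mean AST or ALT > 3.0 × ULN.

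| Baseline state | Synopsis (B or T) | Section 3.3.2 (B and T) |
|---|---|---|
| Neither | Eligible | Eligible |
| B only | Excluded | Eligible |
| T only | Excluded | Eligible |
| Both | Excluded | Excluded |

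The rules disagree in two of the four rows. As an example, ALT of 10 × ULN with normal bilirubin is excluded by the synopsis and eligible under Section 3.3.2.

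**2. Which text governs.** Section 4.1.5 points to Section 3.3, so the *and* version is the one that sites are told to apply.

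**3. Whether another criterion sets a cap.**

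- Inclusion 6 requires recovery to Grade ≤ 1 or baseline, but only from adverse events of prior cancer therapy.
- Exclusions 15 and 27 concern infection and viral hepatitis.
- No other item limits AST, ALT or bilirubin.

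**4. What was probably meant.**

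- The laboratory criterion just before it in Section 3.3.2 uses *or* where any one abnormality should exclude: "20. ANC $< 1.5 \times 10^9/L$ or platelet count $< 100 \times 10^9/L$ or hemoglobin $< 8.0 \text{ g/dL".
- The label in Appendix 6 (section 2.3) withholds pembrolizumab for AST or ALT above 3 and up to 5 × ULN. It lists "AST or ALT greater than 5 times ULN or total bilirubin greater than 3 times ULN" as a reason to stop permanently.
- The label (section 8.7) says that pembrolizumab has not been studied with bilirubin above 1.5 × ULN.

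All of these fit *or* better than *and*. None of them states the intent.

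**5. Consequence for the DLT review.** With six subjects, one event is 1/6 = 16.7% and two are 2/6 = 33.3%, which meets the ≥ 33% threshold for failing the review. This is true of any kind of event, so it shows how sensitive the review is. It does not measure the effect of criterion 21.

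**6. After correction.** Replacing *and* with *or* in Section 3.3.2 makes the two columns of the table agree in all four rows.

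**The case against.** The difference in wording cannot be disputed. What can be disputed is how much follows from it.

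- **The semicolon before *and* could be read as listing two separate grounds for exclusion.** This is strained. The synopsis also has a semicolon, followed by *or*, and criterion 20 uses *or* for the same purpose. If the reading were available, the wording would still be ambiguous and would still need correcting.
- **The limits in Appendix 6 and Table 3-3 apply on treatment.** Table 3-3 covers drug-related adverse events, and a pre-dose value is not one. This stands. A subject who enters above 5 × ULN would not automatically trigger the stopping rule. The limits show only what is treated as unsafe during therapy.
- **Footnote a of Table 3-3 provides for patients with liver metastasis who start with Grade 2 AST or ALT.** If Grade 2 corresponds to the label's band of 3 to 5 × ULN, which is an inference, the footnote sits poorly with a strict 3.0 × ULN cap. This also stands, and it means that the intended rule is not certain. The footnote follows label text and gives no support to having no cap at all.
- **The DLT definition excludes events clearly due to comorbidities and transient laboratory changes without clinical significance.** This reduces the risk of misattribution but leaves it to the investigator's judgement.
- **Randomisation balances baseline liver abnormality in expectation, and laboratory shift tables are planned.** This limits bias in comparisons between arms. It does not protect the individual subject, and it does not help the DLT review or the toxicity stopping rule, which use Arm 2 alone.

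**Conclusion.** The concern holds. The current protocol gives two incompatible versions of criterion 21, and the looser one is in the section used for eligibility. As written, Section 3.3.2 admits isolated transaminase elevation and isolated hyperbilirubinaemia with no upper limit, in a trial with a recognised transaminase risk.

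The certain part is logical: the rules disagree in two of four baseline states, and no other criterion closes the gap. The number of subjects in those two states cannot be estimated from the documents, so no size can be put on the effect on DLT counts or hepatic discontinuations. The argument for *or* rests on criterion 20, the label limits and the known hepatic risk. The protocol does not declare its intent. The correction must be made because subject safety depends on it, whatever the size of any effect on the analysis.

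**What to change.** State one rule for criterion 21 in both the Study Synopsis and Section 3.3.2. If the synopsis carries the intended rule, change *and* to *or* in item 21 of Section 3.3.2. Check the result against Table 3-3 and Appendix 6. If subjects with liver metastasis may enter with higher AST or ALT, write that exception into the criterion with its own numerical ceiling, so that footnote a of Table 3-3 and the entry rule agree.

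Send a letter to sites stating the rule in force. Check the baseline chemistry of subjects already enrolled for AST or ALT above 3.0 × ULN alone, or bilirubin above 1.5 × ULN alone, and identify any such subjects when hepatic events and DLTs are reviewed.

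The cost is one word in the next amendment (a sentence more if an exception is kept), a site letter and a review of laboratory data already collected. Sample size and stopping boundaries do not change.
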